### Clinical Status Assessed on an 8-Point NIAID Ordinal Scale

Number and percentages of subjects within each category of the 8-point NIAID ordinal scale will be summarized by visit for each treatment group. Number and percentages of subjects with an improvement from baseline of  $\geq 2$  points will be analyzed by visit using descriptive statistics as specified in Section 7.

A bar chart showing the frequencies in each category of the scale in the segments of each bar for the two treatment groups by visit will be provided.

### **Hospital Length of Stay**

Hospital LOS will be defined as the time interval from randomization to hospital discharge alive. Survival status will be obtained from the AE CRF as absence of an SAE with outcome “Death Related to Adverse Event”. In this analysis, for subjects who did not have a recorded date of hospital discharge and did not die, the time to hospital discharge will be censored at the last known in-hospital date if the subject did not complete the 28-day Treatment Period (i.e., the date of premature study discontinuation). For subjects who do not have a hospital discharge event or censoring time within the 28 days after randomization or for subjects who have died, an administrative censoring will be applied at 28 days.

Hospital LOS will be analyzed using Cox proportional hazard model including age as a continuous covariate, treatment group, gender (male or female), country (USA or Brazil), and baseline comorbidities (yes or no) as categorical covariates in the model. The hazard ratio, its 95% CI and 1-sided Wald p-value will be estimated from the model. Cumulative event rates will be calculated using the Kaplan-Meier (KM) method. The effect over time will be illustrated with a plot of the complement (1 – KM) of the KM estimates. Event counts and percentages will be summarized. If ties occur, Efron’s method will be used to adjust for ties.

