6.4 Discontinuation of Study Treatment and Subject Withdrawal

6.4.1 Early Discharge from the Hospital

All subjects who maintain consent will remain in the study through Day 28 for all important safety and efficacy assessments. All Day 28 assessments will be conducted on the day of discharge from the hospital. For subjects who are discharged before Day 28, the investigator (or delegate) will contact them via weekly telephone calls. If the telephone call is performed by non-medical study personnel, the information on clinical status, AEs, and changes in concomitant medications need to be reviewed by the investigator or a medically trained delegate. These subjects will be scheduled for an in-person visit on Day 28 to perform the End of Study (EOS) Visit assessments including CCI [REDACTED] and other laboratory parameters.

Every effort will be made to encourage both subject and investigators to continue study assessments via telephone following hospital discharge, unless the subject withdraws consent.

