10.5 Follow-up of Adverse Events

Every effort should be made to follow AEs until resolution or stabilization. Ongoing, nonserious AEs that have not resolved or stabilized will be followed until the subject completes the study. SAEs will be followed until the AE resolves, stabilizes, or the subject is lost to follow-up.

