### **10.2 Analysis of Secondary Endpoints**

Secondary Efficacy Endpoints are:

- All-cause mortality: calculated as number of deaths of any cause from randomization to Day 28 divided by the number of subjects in the treatment group. All deaths will be entered as SAEs in the AE CRF. Thus, the information will be obtained from the AE CRF as SAEs with outcome “Death Related to Adverse Event” and SAE end date (death date) occurring within the 28 days of the Treatment Period.
- Incidence of tracheal intubation from randomization to Day 28: calculated as number of subjects experiencing intubation from randomization to Day 28 divided by the number subjects in the treatment group. Tracheal intubation is defined as presence of a record for this procedure (“Endotracheal Intubation” ticked on the Respiratory Support CRF) with a start date during the 28 days of the Treatment Period.
- Proportions of subjects using CPAP or BiPAP: calculated as number of subjects using CPAP or BiPAP within 28 days of randomization divided by the number subjects in the treatment group. Use of CPAP or BiPAP is defined as presence of a record for this procedure (“CPAP” or “BiPAP” ticked on the Respiratory Support CRF) with a start date during the 28 days of the Treatment Period.
- Proportion of subjects using HFNC: calculated as number of subjects using HFNC within 28 days of randomization divided by the number subjects in the treatment group. Use of HFNC is defined as presence of a record for this procedure (“HFNC” ticked on the Respiratory Support CRF) with a start date during the 28 days of the Treatment Period.

- Proportion of subjects using ECMO: calculated as number of subjects using ECMO within 28 days of randomization divided by the number subjects in the treatment group. Use of ECMO is defined as presence of a record for this procedure (“ECMO” ticked on the Respiratory Support CRF) with a start date during the 28 days of the Treatment Period.
- Clinical status assessed on an 8-point NIAID ordinal scale as entered in the CRF.
- Length of hospital stay defined as time interval from randomization to hospital discharge alive. The information will be derived from the SARS-CoV-2 CRF along with the AE CRF for the survival status (no SAE with outcome “Death Related to Adverse Event” reported).
- Subject’s maximum SOFA score, subject’s maximum change from baseline in SOFA score, and subject’s mean SOFA score during the study will be calculated.

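### Hospital length of stay: the rule for deaths is not compared with the discharge date, so a subject discharged alive who dies by Day 28 can lose a valid discharge event

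*SAP*

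**What the plan says.** The SAP section on Hospital Length of Stay (within 10.2.1) sets the endpoint: "Hospital LOS will be defined as the time interval from randomization to hospital discharge alive". Three operating rules follow.

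- **Survival status.** "Survival status will be obtained from the AE CRF as absence of an SAE with outcome" of death. SAP 10.2 gives the same derivation: "The information will be derived from the SARS-CoV-2 CRF along with the AE CRF for the survival status", with alive meaning that no fatal SAE is reported. Neither place mentions the date of death.
- **Censoring before Day 28.** This applies "for subjects who did not have a recorded date of hospital discharge and did not die" and who left the study early.
- **Censoring at Day 28.** This covers subjects with neither a discharge event nor a censoring time in the 28 days, "or for subjects who have died, an administrative censoring will be applied at 28 days".

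Protocol 11.4 has the same definition and the same Day 28 clause, but not the survival-status sentence. The analysis is a Cox model with the complement of the Kaplan-Meier curve, and the summary measure listed is the median stay.

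**The concern.** Holding subjects who die in hospital at Day 28 is a recognised way to stop an early death from looking like a short stay, and it is not in question here. The difficulty is the subject who leaves hospital alive and dies afterwards. That subject met the endpoint on the day of discharge. The survival rule looks only at whether a fatal SAE exists, and the censoring clause names those who have died as a group of its own. Both point to removing the event, on the strength of something that happened later.

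At stake are the discharge curve, the median stay and the hazard ratio. If post-discharge deaths differ between arms, part of that difference would appear as a difference in length of stay.

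**Working it through.** **1. No figure to reproduce.** Neither document states an expected stay, hazard ratio or post-discharge death rate. The check is a reading of the rules, then an illustration on assumed data.

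**2. One subject through the rules (assumed dates).** Discharged alive on Day 8, dies on Day 20.

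| Rule | Result |
|---|---|
| Endpoint definition | Event at Day 8 |
| Survival status, SAP 10.2 and 10.2.1 | Fatal SAE exists, so not alive |
| Early-censoring rule | Not applicable: discharge date exists and subject died |
| Day 28 clause, SAP 10.2.1 and Protocol 11.4 | Subject has died: censored at 28 |

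The first row and the last conflict, and no sentence gives the earlier discharge precedence.

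**3. Can the case arise?** Yes. Protocol 6.4.1 says: "For subjects who are discharged before Day 28, the investigator (or delegate) will contact them via weekly telephone calls", and schedules an in-person visit on Day 28. SAP 10.1 and 10.2 say that every death is entered as an SAE. A post-discharge death by Day 28 would therefore reach the data that the rule reads.

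**4. How the SAP treats death elsewhere.** All-cause mortality requires an "SAE end date (death date) occurring within the 28 days of the Treatment Period". The primary endpoint also dates deaths (SAP 10.1). Only the length-of-stay survival rule has no date.

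**5. Size at the planned 62 per arm (assumed data).** Each arm has 50 live discharges at identical times and 12 subjects censored at Day 28. Discharge times are t_i = round(3 − 7·ln[1 − q_i(1 − e^(−23/7))]), with q_i = (i − 0.5)/50 for i = 1 to 50. The true hazard ratio is 1.00 and both medians are 9 days. Now let k discharged subjects in one arm, evenly spaced in the ordering, die later and be recoded as written. The hazard ratio is that arm against the other, from a Cox model with Efron ties and treatment only.

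| k | Discharged in that arm | HR | Median in that arm (days) |
|---|---|---|---|
| 0 | 50/62 = 80.6% | 1.00 | 9 |
| 1 | 49/62 = 79.0% | 0.96 | 10 |
| 2 | 48/62 = 77.4% | 0.92 | 10 |
| 3 | 47/62 = 75.8% | 0.88 | 10 |
| 4 | 46/62 = 74.2% | 0.85 | 10 |
| 6 | 44/62 = 71.0% | 0.79 | 11 |

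With dates compared, the k = 0 row holds throughout.

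**6. Large-sample version (assumed rates).** Lognormal stay with median about 9 days, 10% in-hospital death, identical discharge process in both arms; HR is CSL312 versus placebo.

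| Post-discharge death, placebo vs CSL312 | HR as written | HR with dates compared |
|---|---|---|
| 5% vs 2% | about 1.07 (1.06 to 1.08 across repeat runs) | 1.00 |
| 8% vs 2% | about 1.14 | 1.00 |
| 4% vs 4% | about 1.00 | 1.00 |

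**7. Against sampling error.** With about 50 events per arm, SE(log HR) ≈ √(1/50 + 1/50) = 0.20, so a 95% interval multiplies and divides the HR by e^(1.96 × 0.20) ≈ 1.48. The 5% versus 2% shift is ln(1.07)/0.20 = 0.068/0.20 ≈ 0.34 SE. It corresponds to roughly 0.05 × 62 ≈ 3 deaths against 0.02 × 62 ≈ 1.

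**The case against.** **The text can be read more kindly.** A subject sent home alive meets the definition that day, and censoring normally applies to subjects without an event. The Day 28 sentence opens with subjects lacking a discharge event, so its mention of deaths may be meant for deaths in hospital. This reading is probably the intent. It is stronger in Protocol 11.4, which lacks the survival-status sentence. But the SAP spells out how to derive alive, and that derivation points the other way. Two programmers could produce different event counts from the same text.

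**The effect is small and conditional.** This stands. Bias in the hazard ratio needs a difference between arms in post-discharge deaths, the documents supply no rate, and 8% versus 2% is an extreme assumption. SAP 10.3 names one confirmatory test and treats all others as descriptive, so no error rate or sample size depends on this endpoint.

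**Two stronger readings go too far.**

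- A reader might infer that a fatal SAE dated after Day 28 also cancels a discharge, since the survival rule is undated and Protocol 10.5 says that "SAEs will be followed until the AE resolves, stabilizes, or the subject is lost to follow-up". That sentence requires follow-up; it does not say that late outcomes enter the AE CRF. Protocol 10.4 and 10.6.2 keep related SAEs that arise after the final visit out of the eCRF. For a subject no longer participating, 10.6.2 sends follow-up information to the sponsor. The documents mostly route such outcomes away from the data that the rule reads.
- A reader might infer that the analysis ceases to measure length of stay, or merely repeats mortality. Everyone except those discharged alive who later die is handled as intended. In-hospital deaths already enter the endpoint by design.

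**Conclusion.** The point holds for deaths after a live discharge and by Day 28. Followed literally, the SAP's survival derivation and the Day 28 clause remove a real discharge event and contradict the stated endpoint. This is more than a missing detail, because a written rule gives the wrong result for an identifiable kind of subject whom the trial's own follow-up would detect.

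The consequence is modest. There is none if no discharged subject dies, and the hazard ratio barely moves if such deaths are equally frequent in both arms. Under the assumed scenarios, the shift is to about 0.92 for two deaths in one arm of 62, and to about 1.07 and 1.14 for the two unequal large-sample rates. These sizes depend on the assumed stay distribution and death rates. The conflict between the rules does not. The primary analysis is untouched.

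**What to change.** In SAP 10.2 and 10.2.1, replace the undated survival rule with a comparison of dates: a discharge that precedes death is an event on the discharge date. Limit the Day 28 censoring for death to subjects who die before discharge, and make the same limitation in Protocol 11.4. Mortality needs no change, because deaths after discharge within the 28 days are already counted there.

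The cost is one derivation rule and a sentence or two of text. Both dates come from CRF pages that SAP 10.2 already names. No new data are needed, and sample size and the primary analysis stay as they are. The wording should be settled before final unblinding.

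It would also help to report how many subjects in each arm died after a live discharge, so that a reader can see whether the rule mattered.

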### **Sequential Organ Failure Assessment**

The SOFA score assesses organ failure. A subject who does not fall into grade 1 to 4 in any of the components will be assigned a grade 0, representing no organ failure. The SOFA score is calculated as the summation of the six components grades. For the component ‘Respiration’, the grade for partial pressure oxygen (PaO2)/ fraction of inspired oxygen (FiO2) ratio (mmHg) will be used, if it is missing, the grade for peripheral arterial oxygen saturation (SaO2)/FiO2 ratio (mmHg) will be used.

Maximum SOFA score, maximum change from baseline in SOFA score, and mean SOFA score during the study will be calculated for each subject and summarized descriptively as specified in Section 7 by treatment group. Median differences in maximum SOFA score, maximum change from baseline in SOFA score, and mean SOFA score during the study between treatment groups and 95% CIs using Hodges-Lehmann’s method will be reported. Non-parametric Wilcoxon rank-sum test will be used to compare the 2 treatment groups.

The SOFA score and its components will be summarized by treatment and visit using descriptive statistics as specified in Section 7 for the grades and change from baseline in the grades:

- Respiration;
- Coagulation;
- Liver;
- Cardiovascular;
- Central Nervous System;
- Renal.

The observed values of the laboratory tests, vital signs, respiratory, cardiovascular, or central nervous system assessments along with changes from baseline of the individual components which feed into the SOFA score will be summarized by treatment and visit using descriptive statistics as specified in Section 7 in the corresponding sections of the Safety analysis.

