2.2.2 Secondary Endpoints

Secondary Objectives	Endpoints	Summary Measures
1	All-cause mortality	Proportion of deaths from all causes occurring from randomization to Day 28
1	Incidence of tracheal intubation	Proportion of subjects intubated from randomization to Day 28

Secondary Objectives	Endpoints	Summary Measures
1	Clinical status as assessed on an 8-point National Institute of Allergy and Infectious Diseases (NIAID) ordinal scale (Appendix 3)	
 • Number and proportion of subjects with ≥ 2-point improvement in the ordinal scale • Number and proportion of subjects within each of the categories of the ordinal scale
1	Use of continuous positive airway pressure (CPAP) or bi-level positive airway pressure (BiPAP)	Proportion of subjects using CPAP or BiPAP
1	Use of high-flow nasal cannula (HFNC)	Proportion of subjects using HFNC
1	Use of extracorporeal membrane oxygenation (ECMO)	Proportion of subjects requiring ECMO
1	Change in Sequential Organ Failure Assessment (SOFA) score (Appendix 2)	
 • Median of maximum change from Baseline in SOFA score • Change from Baseline in SOFA score and in the individual components of SOFA score
1	Hospital length of stay (LOS)	
 • Median LOS in hospital stay

Secondary Objectives	Endpoints	Summary Measures
2	Subjects experiencing the following safety events: 
 • Adverse events (AEs) • Serious adverse events (SAEs) • Adverse events of special interest (AESIs) • CSL312-induced anti-CSL312 antibodies • Clinically significant abnormalities in laboratory assessment that are reported as AEs 	Number and proportion of subjects experiencing the specified safety events after treatment with CSL312 or placebo
3	CSL312 PK in plasma: 
 • Maximum plasma concentration (C_{max}) • Time to maximum plasma concentration (T_{max}) • Area under the plasma concentration-time curve from time zero to the time of the last measurable concentration (AUC_{0-last}) • Terminal half-life ($T_{1/2}$) 	
 • Mean (\pm SD) and geometric mean (geometric coefficient of variation percentage [CV%]) for all PK parameters except T_{max}. • Median (minimum, maximum) for T_{max}

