Maximum SOFA score, maximum change from Baseline in SOFA score, and mean SOFA score during the study will be calculated for each subject and summarized by treatment group. Descriptive statistics for continuous variables will be reported. Median differences between treatment groups and 95% CIs using Hodges-Lehmann's method will be reported. Nonparametric Wilcoxon rank-sum test will be used to compare the 2 treatment groups. SOFA score components will also be summarized by treatment and visit using descriptive statistics.

The ITT Analysis Set and mITT Analysis Set will be used for the secondary efficacy endpoint analyses.

Baseline is defined as the most recent, non-missing value before randomization, if applicable, otherwise, the most recent non-missing value before administration of IP.

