## 4.3 Randomization Procedures and Blinding

Randomization and blinding procedures are described in the protocol. Randomization will be conducted using an interactive response technology (IRT). Subjects will be randomly assigned to treatment with either CSL312 + SOC or placebo + SOC using a 1:1 randomization ratio and stratified by country (USA or Brazil). A centralized randomization schedule will be used. The randomization list will be generated according to the approved randomization specifications. The IRT service provider will keep the randomization code on file.

Study unblinding will take place after database lock, except in the situations as outlined in protocol sections 5.1.3.2, 5.1.3.3, and 5.1.3.4 related to emergency unblinding and unblinding for safety reasons.

Adequate procedures are in place to ensure the integrity of the blinded data within CSL. Study data will be provided to the IDMC as unblinded data.

The analyses planned for the IDMCs are described in a separate IDMC SAP.

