### **8.2.4 Change from Baseline**

Change from baseline is calculated as:

- visit value - baseline value.

Percentage change from baseline is calculated as:

- $(\text{change from baseline} / \text{baseline value}) * 100$ .

If either the baseline or visit value is missing, the change from baseline and percentage change from baseline will also be missing.

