### 10.1.2 Primary Efficacy Analysis

The primary endpoint for this study is the risk of tracheal intubation or death prior to tracheal intubation from randomization to Day 28. The ITT Analysis Set will be used for the primary efficacy analysis.

Subjects with less than 28 days of the Treatment Period (i.e., who discontinued from the study prematurely) and without documented intubation or death will be considered to not have progressed to tracheal intubation or died prior to tracheal intubation (see Section 10.1.3).

Firth logistic regression model including age as continuous covariate, treatment group, gender (male or female), country (USA or Brazil), and baseline comorbidities (yes or no) as categorical covariates in the model will be used to compare the risks of progression between the 2 treatment groups. Comorbidities will include hypertension, diabetes, and obesity (defined as BMI  $\geq 30$  kg/m^2). A 1-sided p-value will be estimated from the model and the null hypothesis (see Section 4.1.2) will be rejected if that p-value is  $< 0.025$ . The risk difference and associated 2-sided 95% confidence interval (CI) will be estimated using the method described by [Ge et al \[2011\]](#).

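### The SOFA comparisons leave out the country stratum and make little or no use of baseline SOFA, which costs precision on a descriptive secondary endpoint

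*SAP*

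**What the plan says.** SAP 10.2.1, under Sequential Organ Failure Assessment, derives three measures per subject: "Maximum SOFA score, maximum change from baseline in SOFA score, and mean SOFA score during the study will be calculated for each subject". For the comparison it says: "Non-parametric Wilcoxon rank-sum test will be used to compare the 2 treatment groups". The effect estimate is a median difference "between treatment groups and 95% CIs using Hodges-Lehmann’s method will be reported". Protocol 11.4 has the same test: "Nonparametric Wilcoxon rank-sum test will be used to compare the 2 treatment groups". No stratum or covariate is named for the test or the interval.

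Randomisation is done "using a 1:1 randomization ratio and stratified by country (USA or Brazil") (SAP 4.3; likewise Protocol 5.1.2). The primary analysis in SAP 10.1.2 is a "Firth logistic regression model including age as continuous covariate, treatment group, gender (male or female), country (USA or Brazil), and baseline comorbidities (yes or no"). The five binary secondary endpoints use that same model, and hospital length of stay uses a Cox model that also contains country.

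The endpoint table in Protocol 2.2.2 lists, first for SOFA, "Median of maximum change from Baseline in SOFA score". SAP 8.2.4 defines change as "visit value - baseline value". SAP 10.3 names one confirmatory test and treats all others as descriptive.

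**The concern.** SOFA is the one tested efficacy endpoint visible in the documents whose analysis omits the randomisation stratum, and no reason is given. Baseline SOFA has to be available for the change score, yet maximum and mean SOFA are compared without it. If baseline severity predicts later severity, that between-subject variation stays in the comparison as noise.

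A chance baseline imbalance also goes uncorrected. It would push the raw score and the change score in opposite directions, so the three SOFA results could disagree for that reason alone.

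What is at stake is the width of the SOFA intervals and how readable these results are in a trial of about 124 subjects.

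**Working it through.** **The plan's own figure.** The documents give no power statement for SOFA. The stated 124 belongs to the primary endpoint (30% versus 10%, 80% power, one-sided 0.025). It reproduces:

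n per arm = [1.96·√(2·0.2·0.8) + 0.842·√(0.3·0.7 + 0.1·0.9)]² / 0.2² = (1.109 + 0.461)² / 0.04 = 61.6, so 62 per arm, with power 80.3%. It says nothing about SOFA.

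**Inputs.** From the documents: 62 per arm, 1:1 allocation within country, one-sided 0.025. Assumed, because the documents are silent: treatment effect 0.45 SD; baseline-outcome correlation ρ of 0.3, 0.5 or 0.7; equal SDs at baseline and afterwards; 60/40 country split; country difference 0 or 0.5 SD.

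**Variance ratios (large sample).**
- Adjusted versus raw score: 1 − ρ² = 0.91, 0.75, 0.51. Adjustment removes 9%, 25% or 49% of the variance.
- Adjusted versus change score: (1 − ρ²) / [2(1 − ρ)] = (1 + ρ)/2 = 0.65, 0.75, 0.85. Adjustment removes 35%, 25% or 15%.
- Change versus raw score: 2(1 − ρ) = 1.4, 1.0, 0.6. Below ρ = 0.5, subtracting baseline adds noise.
- Country: share removed = f(1 − f)d² / [1 + f(1 − f)d²]. With f = 0.4 and d = 0.5 this is 0.06/1.06 = 5.7%. With d = 0 it is nil.

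**Power by formula.** For a rank test on normal data the standardised effect is 0.45·√31·√(3/π) = 2.45. Power is Φ(2.45/√v − 1.96), where v is the variance relative to the raw score.
- Raw score, v = 1: 69%.
- Change, v = 1.4, 1.0, 0.6: 54%, 69%, 89%.
- Adjusted, v = 0.91, 0.75, 0.51: 73%, 81%, 93%.

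**Power by simulation.** 6,000 trials per setting, 74 and 50 subjects in the two countries, scores rounded to integers. Rounding and ties bring the figures a few points below the formula. Each cell gives power with no country difference / with a 0.5 SD difference.

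| ρ | Plain test, raw score | Plain test, change | Country-stratified rank ANCOVA on baseline |
|---|---|---|---|
| 0.3 | 67.3% / 64.1% | 52.7% / 51.6% | 70.2% / 68.2% |
| 0.5 | 68.3% / 64.1% | 66.5% / 64.8% | 77.2% / 77.1% |
| 0.7 | 67.7% / 64.4% | 86.0% / 83.2% | 88.7% / 88.5% |

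Stratifying the Wilcoxon test by country, without baseline, changed power by −0.2 to −0.6 points with no country difference and by +1.3 to +2.5 points with a 0.5 SD difference. With no treatment effect, rejection rates ran from 1.8% to 2.7% for the plain test and from 2.2% to 2.9% for the adjusted test, against a nominal 2.5% (simulation standard error 0.2 points).

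**Chance imbalance.** The baseline difference between arms has standard error √(2/62) = 0.18 SD. At ρ = 0.5, an imbalance of that size moves the raw-score difference by 0.5·0.18 = 0.09 SD and the change-score difference by (0.5 − 1)·0.18 = −0.09 SD. Each is a fifth of the assumed effect.

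**The case against.** A reader might infer that the SOFA comparisons ignore baseline altogether. The documents do not support that: maximum change, the first summary measure listed for the endpoint, subtracts it. If ρ is about 0.7, the change score already captures most of what adjustment offers (86% against 89%).

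A reader might also infer that leaving out the stratum invalidates the test. It does not. Ignoring a stratum used in 1:1 randomisation makes the test at most slightly conservative, and the simulated departures from 2.5% are small.

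Three further objections carry weight:
- Every input to the power figures is assumed. Subjects are not intubated at randomisation, so real SOFA scores may be low, skewed and heavily tied.
- Consistency with the plan's other models argues only for country. None of the Firth or Cox models contains baseline SOFA, so adding it is an efficiency argument and not the repair of a contradiction.
- The tests are descriptive and no decision hangs on them. SOFA is also summarised by arm and visit, so a baseline imbalance would be visible.

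These limit the size and urgency of the point. They do not remove it: the plan reports an estimate, an interval and a test for SOFA, and the unused information must be in the database anyway. Seeing an imbalance is also not the same as correcting for it, and an adjustment chosen after unblinding would be open to question.

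**Conclusion.** The point holds as a loss of precision. The planned test is valid, shows no inflation of type I error, and has no bearing on the primary result. Nearly all the recoverable precision lies in baseline SOFA; the country part is mainly a matter of analysing as randomised.

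Under the assumed 0.45 SD effect and 62 per arm, power for maximum or mean SOFA would go from about 66% to about 69%, 77% and 89% at correlations of 0.3, 0.5 and 0.7. For maximum change, about 53%, 66% and 86% would go to the same values. The gain therefore runs from about 3 points to more than 20, depending on a correlation that the documents do not give. The direction is secure; the size is not.

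**What to change.** In SAP 10.2.1 and Protocol 11.4:
- Pre-specify, for the three SOFA measures, a rank analysis of covariance stratified by country with baseline SOFA as covariate.
- Report an effect estimate and 95% CI adjusted for the same two factors, for example by inverting the same test over location shifts. An interval stratified by country alone would not match the adjusted test.
- State how a missing baseline SOFA is handled, for example by simple imputation within country, so that no randomised subject drops out of the maximum and mean comparisons.
- Keep the planned Wilcoxon and Hodges-Lehmann results beside it.

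The cost is SAP and protocol wording, a little more programming and the missing-baseline rule. No new data are needed. The choice should be fixed before unblinding.
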